Yeager and colleagues have developed brief interventions aimed to change entity theories by means of efficient and persuasive intervention tactics that are based on the above mentioned mechanisms. For instance, in one of these interventions, a six-session high school classroom intervention teaching an incremental theory reduced aggressive behavior by 40%, improved depressive symptoms two weeks post-intervention, and increased school attendance (Yeager, Trzesniewski, & Dweck, 2013). Later, they tested the effects of a shorter intervention consisting of only one session. This single session touch an incremental theory via computers. In this session 9th grade students read a scientific article about the possibility of personality change, then they read quotes from older students transmitting the same message. Finally, the students

wrote a brief essay where they defended the same idea with the aim of transmitting the message to other students in the future. Despite the brevity of this intervention, the results obtained by means of a double-blind randomized experiment showed that it reduced levels of self-reported clinically relevant depression (Miu & Yeager, 2014) and stress levels (Yeager et al., 2014).

II. AIMS AND HYPOTHESES

Aim 1: To replicate the effect of an intervention based on Implicit Theories of Personality (ITP) on depressive symptoms (Study 1) and aggressive behavior (Study 2) in a large sample of Spanish adolescents. Grounded on the previous findings obtained in US samples, we will test the efficacy of the ITP intervention by comparing changes in depressive symptoms and aggressive behavior from pretreatment to follow up between the group receiving the ITP intervention and a control group that will receive a control educational condition.

Hypothesis: Those adolescents receiving the ITP intervention will show fewer symptoms of depression and lower frequency of aggressive behavior than the control group after the intervention and at six-month and one-year follow-up.

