Aim 2: To test whether the intervention changes biological and cognitive variables. From a biopsychosocial perspective, several mechanisms can explain the effect of the ITP intervention on psychological problems (depression and aggressive behavior). These mechanisms include changes in cognitive vulnerabilities and changes in the biological responses to the environmental stressors. If participants develop beliefs that personality traits are malleable, this should influence many maladaptive cognitive schemas. In fact, a feature of most maladaptive cognitive schemas is their absolute and stable nature (e.g., "I am a bad person", "The others will always reject me", "People hurt me on purpose", "I cannot put limits to my conduct". The intervention could also change biological indicators of stress (e.g., hormonal indicators). Therefore, in this project we will evaluate whether the ITP intervention affects cognitive vulnerabilities and biological indicators (cortisol, testosterone and DHEA in saliva).

Hypothesis: the association between the intervention and changes in psychological problems will be associated with changes in cognitive and hormonal variables. Some studies have explored whether the effects of interventions on depressive symptoms are mediated by changes in cognitive vulnerabilities with mixed results (Mychailyszyn et al., 2012). Thus, this project aims to contribute to clarifying mediational cognitive mechanisms.

Aim 3: To identify whether development and sex moderates the effects of the intervention. Regarding the developmental stage at which the preventive intervention is more effective, though studies are inconclusive, in general there is some consensus that cognitive vulnerabilities tend to consolidate in adolescence. Also in the case of

depression prevalence rates increase dramatically during adolescence. This supports the tentative hypothesis that the preventive intervention may be more effective if implemented early (i.e., before depression rates increase and cognitive vulnerabilities are consolidated).

As girls display higher rates of depression and boys higher rates of some modalities of aggressive behavior, sex could moderate the effects of the ITP intervention on psychological problems. For instance, we hypothesize that the ITP intervention will lead to a higher reduction of depressive symptoms in girls.

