Aim 4: To test whether temperament moderates the effect of the intervention. We hypothesize that the intervention will be more effective in adolescents high in neuroticism.

III. METHODS

This project will use a randomized controlled trial study design with pretest, posttest, six-month follow-up, and one-year follow-up. Group 1 (experimental group) will receive the ITP intervention and Group 2 (control group) will receive an educational intervention.

Study design and participants

We will conduct a double-blind randomized controlled trial (RCT) with two parallel groups in a large sample of volunteer adolescents (approximately n=900), from several high school centers (ages from 12 to 18 years). The schools will be randomly selected from the Basque Country. Participants will be randomly assigned to the experimental vs control groups. Group assignation will be done at the individual level within each classroom. Participants were randomized in a 1:1 ratio blocked by gender to one of two groups (experimental versus control condition). They were assigned to their allocated group in class by the researchers.

Measures

Depressive symptoms and aggressive behavior will be assessed by means of self-reports through the Center for Epidemiologic Studies Depression scale (CES-D; Radloff, 1977), the revised version of the Peer Experiences Questionnaire (RPEQ; Prinstein, Boergers, & Vernberg, 2001), the Cyber Bullying Questionnaire (CBQ; Calvete, Orue, Estévez, Villardón, & Padilla, 2010; Gámez-Guadix, Villa-George, & Calvete, 2014).

Measures of cortisol, DHEA and testosterone in saliva: A subset of the participants (around 50%) will provide saliva samples to be assayed for neuroendocrine levels to measure cortisol, DHEA and testosterone. Saliva samples will be collected at baseline (one week before the intervention), post-intervention (one week after the intervention) and at the two follow-ups (six-months and one-year follow-up). Data collection will occur in school and the time of assessments will remain

the same for each individual to minimize the effects of diurnal rhythms and reduce error variance. The adolescents will complete an intake survey (e.g., eating, drinking, exercise, and medication) that can potentially affect hormonal reactivity. The adolescents will then be directed to transfer saliva from their mouths to a tube. The sample tubes will be carefully labelled. As soon as the session ends, saliva samples will be sent to the assay laboratory.

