Cognitive vulnerabilities: Two important cognitive vulnerabilities will be assessed: dysfunctional cognitive schemas and beliefs about implicit theories of personality. We will measure cognitive schemas that are relevant for depression (i.e., defectiveness, emotional privation) in the study about depression. We will use the Spanish version of the Young Schema Questionnaire (YSQ; Young, 2006). In addition, we will measure implicit theories of personality through the Implicit Theories of Personality questionnaire (Yeager et al., 2014).

Temperament traits: Temperament will be assessed by the revised version of the Early Adolescent Temperament Questionnaire (EATQ-R; Ellis & Rothbart, 2001) and the Big Five Questionnaire for children (BFQ-C; Barbaranelli, Caprara, Rabasca, & Pastorelli, 2003) for adolescents at the beginning of the study.

Parent reports: Parents will be invited to participate by responding measures about their children temperament by means of the revised version of the Early Adolescent Temperament Questionnaire (EATQ-R; Ellis & Rothbart, 2001) and the Big Five Questionnaire for children (BFQ-C; Barbaranelli et al., 2003) for parents and depressive symptoms through the CBCL 6/18 (Achenbach, 1991; Achenbach & Edelbrock, 1983). These data will be used in analyses in case that the response rate is enough.

Preventive Intervention

The **ITP intervention** lasts one session (of approximately one hour) and has three main parts: (1) scientific information; (2) normative stories from upperclassmen; and (3) self-persuasive writing exercise. In the first part, students read a scientific article that provides evidence that individuals have the potential to change. Participants read about actual neurological and behavioral studies showing that behaviors are controlled by “thoughts and feelings in brains,” and that pathways in the brain have the potential to be changed under the right circumstances. In the second part, participants read several normative quotes purportedly written by upperclassmen that previously read the same article and endorsed its conclusions. These quotes are obtained from previous interventions and edited by the team. These testimonials are provided to bring credibility to the incremental theory. Finally, in the last part, participants will be asked to write their own version of such a narrative to share with future students. This activity has been shown to facilitate the internalization of the intervention message,

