building on a long line of research on cognitive dissonance (Walton & Cohen, 2011). For a more complete description of the ITP intervention see Yeager et al. (2013). The intervention will be adapted to the developmental characteristics of the participants.

The **educational intervention** involves scientific information about the human brain. It was designed to be parallel to the experimental intervention and, hence, it has also three main parts. First, participants are asked to read scientific information about the different areas of the brain and their specialties. Second, participants read several testimonials written by upperclassmen about their transition to high school and how their brains help them to adapt to the new space and all the physical differences of the building and the classes. Finally, participants are asked to write a letter to another student explaining the main things he or she has learned about the brain and thinks are important for adapting to the new physical environment in high school. Hence it will control for the possibility that simple optimism about the potential for growth might account for our results. This is a conservative control group. An entity theory control group would be unethical in a longitudinal field experiment because it could teach the belief that personality cannot be changed, which has been associated to negative consequences.

Procedure

Parental informed consent forms will be sent to parents and adolescents. Those who accept to participate in the study will complete report measures at four waves: (1) one-week before intervention; (2) one-week after intervention; (3) six-months follow-up; and (3) one-year follow-up. Saliva samples will be collected at the same time points. Parents' participants will complete report measures at three waves: (1) one-week before intervention; (2) six-months follow-up; and (3) one-year follow-up. Intervention will be applied one week after the first survey. All the measures will be anonymous and participants will be asked to provide certain data (her/his birth date, first initial of mother's name, and first initial of father's name) to match their questionnaires, saliva samples and intervention tasks over time. Both interventions and assessment measures will be administered by research assistants during normal class time and last around 50 minutes.

Ethical considerations

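### Must the plan fix a mediation model for Aim 2, and name schema scales for the aggression study, before its mechanism analysis can stand?

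*Combined protocol and SAP*

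**What the plan says.** Section II, Aim 2, first asks whether the intervention alters cognitive and hormonal variables, which is a comparison of randomised arms. The hypothesis below it is that "the association between the intervention and changes in psychological problems will be associated with changes in cognitive and hormonal variables". After noting mixed evidence on cognitive mediators of depressive symptoms, the text adds that "this project aims to contribute to clarifying mediational cognitive mechanisms". The background to the aim treats changed cognitive vulnerability as a possible mechanism for both depression and aggression.

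Section III, Measures, says: "Two important cognitive vulnerabilities will be assessed: dysfunctional cognitive schemas and beliefs about implicit theories of personality". It continues: "We will measure cognitive schemas that are relevant for depression (i.e., defectiveness, emotional privation) in the study about depression". The instruments are the Young Schema Questionnaire (YSQ) and an implicit-theories questionnaire. No schemas are named for the aggression study. For the hormones, "A subset of the participants (around 50%) will provide saliva samples". Section III, Procedure, sets four waves (one week before the intervention, one week after, six months and one year) and adds: "Saliva samples will be collected at the same time points".

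Section IV is a single paragraph. It lists mixed ANOVA, multilevel models and regression, leaves the list open, and names SPSS, Mplus, LISREL and HLM. It links no method to any aim.

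**The concern.** Randomisation protects the effect of arm on a mediator. It does not protect the path from mediator to outcome, so a mediation result depends on the model: which wave supplies the mediator, which supplies the outcome, and what is adjusted for. Section IV settles none of this. The wording about change in section II permits a regression of change on change within the same interval, and the structural-equation software equally permits a time-ordered model. If these disagree on the same data, the mechanism conclusion could depend on a choice made after the data are seen.

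The schema measures raise a second question. Aim 2 offers cognitive vulnerability as a mechanism for aggression too, yet the only schemas named are those for depression.

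**Working it through.** The plan states no mediation figure, so there is nothing to reproduce. The check is whether the open choice matters, and whether a clearly better model exists that the plan ought to name.

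**1. Number of possible analyses.** Depression: 6 mediators (2 schemas, implicit-theory beliefs, 3 hormones) × 1 scale = 6 pairs. Aggression: 4 mediators (beliefs, 3 hormones) × 2 scales = 8 pairs. Total 6 + 8 = 14 pairs. With six wave pairings (three same-wave, three lagged), 14 × 6 = 84 possible indirect effects.

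**2. Sample sizes.** About 900 in all. The saliva subset is 0.5 × 900 = 450. If the 900 were split evenly between the two studies (an assumption), the saliva subset of one study would be 225.

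**3. First simulation, no true mediator path.** Assumptions: mediator effect 0.1, 0.2 or 0.3 SD; outcome effect 0.2 SD; stable-trait correlation 0.3 or 0.5; trait share of variance 0.5; same-session correlation 0 to 0.4; 500 replicates per setting. The indirect effect is a × b, where a is arm to mediator and b is mediator to outcome. Mediation is declared when both paths have two-sided p < 0.05.

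- A: baseline-to-six-month change in outcome on the same change in mediator.
- B: six-month outcome on one-week mediator, adjusted for arm, baseline mediator, and baseline and one-week outcome.
- C: the same time order, with random intercepts for mediator and outcome.

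| False mediation | n=900 | n=450 | n=225 |
|---|---|---|---|
| A, same-session correlation 0.1–0.4 | 26–100% | 12–90% | 4–65% |
| A, same-session correlation 0 | 1–6% | 1–5% | 0–6% |
| B, same-session correlation 0.1–0.4 | 2–35% | 1–23% | 1–9% |
| B, same-session correlation 0 | 7–50% | 4–32% | 1–12% |
| C, all settings | ≤7% | ≤7% | ≤7% |
| A and B differ in significance | 8–93% | 5–86% | 1–64% |

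The Monte Carlo standard error is √(0.05 × 0.95 / 500) ≈ 1 point at 5%, and √(0.5 × 0.5 / 500) ≈ 2 points at 50%. A repeat of A and B with separate code (400 replicates) gave disagreement of 11–94%, 2–84% and 2–59%. Model C was not repeated.

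**4. What the disagreement consists of.** It counts trials in which one model is significant and the other is not. Both models were significant with opposite signs in at most about 5% of trials in any setting, and usually in under 1%.

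**5. The condition behind the rates.** Every setting in the table gives the intervention a real effect on both mediator and outcome. With the mediator effect set to 0, A declares mediation in at most 7% of trials and B in at most about 2%.

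**6. Second simulation, different data models.** Effect 0.2 SD, n=900, 1000 trials, interval for a × b. The lagged model adjusts for the one-week outcome, as B does; the same-wave model uses change from baseline to one week.

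| Scenario | Same-wave | Lagged | Differ |
|---|---|---|---|
| True mediation | 43% (mean a × b +0.012) | 96% (mean −0.060) | 53% |
| Reverse causation, no mediation | 19% | 0.8% | 19% |
| Parallel effects, no mediation | 95% | 3.5% | 92% |

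Here the adjusted lagged regression keeps false mediation at 0.8–3.5%, whereas B reached 50% in step 3. The ranking of models depends on the assumed data.

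**7. Is C a safe replacement?** The data in step 3 have the structure that C assumes, which favours it. With an unmeasured time-varying common cause (autocorrelation 0.5, same-session correlation 0.2–0.4), C gives 28–71% false mediation at n=900 and 15–37% at n=450. B gives 60–64% and 27–29%. C can therefore do better or worse than B.

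**8. What does not depend on the choice.** The effect of arm on each mediator is a randomised comparison. For a difference of 0.2 SD, power is Φ(0.2 × √(n/2) − 1.96). With 450 per arm this is Φ(3.00 − 1.96) = 85%. With 225 per arm (the saliva subset) it is Φ(2.12 − 1.96) = 56%. Neither figure changes with the mediation model.

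**The case for a change.** The strongest case for a change is that mechanism is a stated goal, that 84 indirect effects are available, and that none is primary. If any of the six wave pairings in the first simulation may be chosen, at least one shows false mediation in 21–100% of null trials at n=900 and 11–99% at n=450. A same-wave analysis can also miss real mediation: with a true lagged path of 0.2 and no same-session correlation, A finds it in 5% of trials at n=900, against 91–95% for B and C. The decision rule matters too. In the second simulation under true mediation, with a lagged model not adjusted for the one-week outcome, a causal-steps rule declares mediation in 18% of trials and an interval for a × b in 96%. Naming one model would need no new data.

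Much of this stands. The omission is in the text and is not a redaction, and a mechanism claim resting on one model chosen afterwards would be weak. But these figures describe what selective or naive analysis could do; the plan commits to neither. They rest on path values that the documents do not supply, so they show that disagreement is possible and not how likely it is here. Because section IV assigns no method to any aim, Aim 2 is one instance of a generally brief plan and not a particular error.

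On the schemas, section III can fairly be read as confining them to the depression study, and the sentence on mediation follows from evidence about depressive symptoms. On that reading no scale is missing. On the other reading, the aggression study still has implicit-theory beliefs and three hormones as candidate mediators.

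**Conclusion.** The plan does not need to change on this point. The gap is missing detail that analysts can fill sensibly: the four waves place a one-week mediator before a six-month outcome, and Mplus and LISREL fit such models. The efficacy comparison in Aim 1 and the randomised effects on the mediators are unaffected. The concrete alternative, a random-intercept cross-lagged model, is a trade-off: false mediation is at most 7% where its assumptions hold but 28–71% at n=900 under a time-varying common cause. The schema question is one of wording.

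The possible disagreement between models (8–93% at n=900) is large, but it is a difference in significance, almost never a reversal of sign. It arises only under assumed effects on both mediator and outcome. None of the simulations includes dropout, and model C was tested only with the joint-significance rule. What remains is a caution for the reader: Aim 2 is worded as an association, and any mediation result from it should be read as exploratory, with same-wave change associations taken as associations only.

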After completing measures, adolescents will be provided with information on services for adolescents (e.g., phone number of attention to adolescents). From an ethical perspective, the most important care aspect is the protection of information. We will follow the Directive 95/46/EC of the European Parliament, *Ley Orgánica 15/99 de 13 de diciembre de Protección de datos de Carácter Personal*, and of the Council of 24 October 1995 on the protection of individuals with regard to the processing of personal data and the free movement of such data. No identification data, such as names or surnames, will be used; instead, we will use a numeric code to match measures across times and sources (parents, and adolescents). Thus, each adolescent, and only he/she, will know his/her code. We will also follow the procedure for data protection that the University of Deusto has registered in the National Data Protection Agency. The project has been approved by the Ethics in Research committee of University of Deusto.

IV. STATISTICAL ANALYSES PLAN

Descriptive statistics of sociodemographic and study variables will be provided and several statistical strategies will be used to test the hypotheses. These will include mixed analyses of variance (ANOVA), multilevel analyses, regression analyses, among others. We will use IBM SPSS, MPLUS, LISREL, and HLM software for analyses.

References

Achenbach, T. M. (1991). Child Behavior Checklist/4-18 and 1991 profile. *Burlington, Vermont, USA: University of Vermont, Department of Psychiatry*.

Achenbach, T. M., & Edelbrock, C. S. (1983). Manual for the Child Behavior Checklist/4-18 and revised child behavior profile. *Burlington, Vermont, USA: University of Vermont, Department of Psychiatry*.

Blackwell, L. S., Trzesniewski, K. H., & Dweck, C. S. (2007). Implicit theories of intelligence predict achievement across an adolescent transition: A longitudinal study and an intervention. *Child Development*, 78(1), 246-263. doi:10.1111/j.1467-8624.2007.00995.x

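### The plan names no primary model and places classroom, sex or baseline score in none, so it permits a pupil-level ANOVA of change that is less precise and can be too liberal if the effect varies between classes

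*Combined protocol and SAP*

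**What the plan says.** Under Study design and participants (section III), the protocol states "Group assignation will be done at the individual level within each classroom" and "Participants were randomized in a 1:1 ratio blocked by gender to one of two groups". It plans for about 900 adolescents aged 12 to 18 from several schools. It does not say whether the gender blocks were formed inside each classroom or across the whole sample.

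Aim 1 (section II) defines the test as "comparing changes in depressive symptoms and aggressive behavior from pretreatment to follow up between the group receiving the ITP intervention and a control group". Aim 3 is "To identify whether development and sex moderates the effects of the intervention". There are four waves: before the intervention, one week after it, six months and one year.

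Section IV is short. On methods it says "These will include mixed analyses of variance (ANOVA), multilevel analyses, regression analyses, among others", and on software "We will use IBM SPSS, MPLUS, LISREL, and HLM software for analyses". No method is tied to a hypothesis, none is called primary, and no model is written out. Classroom, sex and baseline score are not assigned to any analysis.

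**The concern.** Classroom and gender are features of the randomisation, and every pupil has a baseline score. The plan commits to using none of these in the main comparison. An arm-by-time ANOVA on individual pupils would satisfy section IV as written.

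Two things are at stake:

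- **Precision.** A change-based analysis gives up information that a baseline-adjusted analysis of the same data would use.
- **Error rate.** Pupils in one class are usually close in age, so arm-by-age in Aim 3 is largely a comparison of arm effects between classes. If the arm effect differs from class to class for reasons other than age, a pupil-level test counts pupils where classes are the relevant unit, and its standard error is too small. The same applies to the main effect if the result is meant to extend to classes outside the trial. That is a natural reading, because the schools are to be randomly selected from a region.

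**Working it through.** **Inputs.** From the documents: about 900 pupils, 1:1, individual allocation within classroom, blocking by gender, ages 12 to 18, and a contrast defined on change. The documents give no power calculation, effect size, SD, intraclass correlation (ICC), pre-post correlation, class size or number of classes, so there is no planned figure to reproduce. The values below are assumptions: pre-post correlation ρ of 0.4 to 0.75; class ICC of 0.02 to 0.10; 40 classes of 22 (880 pupils); age constant within class; and a between-class SD of the arm effect, τ, of 0.1 to 0.3 in SD units of the analysed score.

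**Step 1: change score against baseline adjustment.** With equal variance σ² at both waves, a change score has variance 2σ²(1 − ρ). A baseline-adjusted score has residual variance σ²(1 − ρ²). The ratio of standard errors, adjusted to change, is √[(1 + ρ)/2].

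| ρ | SE ratio | SE reduction | Equivalent gain on n = 900, as 900 × 2/(1 + ρ) |
|---|---|---|---|
| 0.4 | √0.70 = 0.837 | 16% | 1,286 |
| 0.6 | √0.80 = 0.894 | 11% | 1,125 |
| 0.75 | √0.875 = 0.935 | 6% | 1,029 |

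**Step 2: leaving out classroom and sex, arm effect constant.** Balance within strata makes the naive standard error too large by a factor 1/√(1 − ICC). The ICC that counts here is that of the change score. Stable class and sex differences cancel in change, so this ICC is smaller than that of the raw score. A change-score ICC of 0.02 gives 1/√0.98 = 1.010, and 0.05 gives 1/√0.95 = 1.026. Simulation of the change contrast at ρ = 0.6 and class ICC 0.02 to 0.10 gave an overstatement of about 1% to 3%. A separate simulation at ICC 0.05 and 0.10 found essentially none (naive to true ratio 0.99 to 1.00).

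**Step 3: arm effect varying between classes.** In a class of m pupils split equally, the arm difference has variance 4/m + τ² (with σ = 1). A pupil-level analysis reflects essentially the first term. The ratio of naive to true standard error is therefore about √[(4/m)/(4/m + τ²)], and the true two-sided error is 2[1 − Φ(1.96 × ratio)]. With m = 22, 4/m = 0.1818.

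| τ | Ratio | Type I error |
|---|---|---|
| 0.1 | √(0.1818/0.1918) = 0.974 | 5.6% |
| 0.2 | √(0.1818/0.2218) = 0.905 | 7.6% |
| 0.3 | √(0.1818/0.2718) = 0.818 | 10.9% |

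The same ratio applies to arm-by-age when age is constant within class, because each class contributes one arm difference to the regression on age.

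Simulations agree:

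- **40 classes of 22:** arm-by-age error was about 7% at τ = 0.2 and about 10% at τ = 0.3. For the main effect on change (ICC 0.05) it was 7.8% and 10.9%.
- **36 classes of 24, raw scores:** at τ² = 0.05 (τ = 0.22), arm-by-age error was 6.9% to 7.8% and main-effect error 6.6% to 8.1%. At τ² = 0.10 (τ = 0.32), they were 11.4% to 11.9% and 10.2% to 11.3%.
- **Class-level analysis of arm-by-age:** error stayed at 4.5% to 5.3% throughout the 36-class runs.

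Simulation error in the 36-class runs is about ±1 percentage point, so the main-effect and arm-by-age ranges are not clearly different from each other.

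**The case against.** The strongest reply is that section IV does not say classroom and sex will be left out. Multilevel analysis stands in the same sentence as ANOVA, HLM and MPLUS can fit it, and sex must enter at least the sex-moderation model of Aim 3. Being first in a list does not make ANOVA the primary analysis. All of this stands. The documents support only that the plan permits an analysis without these terms, not that it has chosen one.

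A reader might also infer three stronger points, which the documents do not support:

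- **That the main-effect standard error is overstated by as much as 8.5%.** That figure is 1/√(1 − 0.10 − 0.05) and describes a raw-score comparison at one time point. Aim 1 tests change, from which stable class and sex differences have already been removed.
- **That the main-effect standard error is too large while the age test's is too small.** These need different conditions. The first requires a constant arm effect across classes and the second a varying one. Once the effect varies enough to distort the age test, the main-effect standard error is also too small for inference to other classes.
- **That the trial expects small effects.** The background reports small average effects for other universal programmes but describes excellent results for this intervention. No expected effect size is stated.

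Finally, the inflation depends on an unknown between-class SD and disappears when that SD is small. With a constant effect, the raw-score simulation found the pupil-level age test slightly conservative (3.5% to 4.0%). This stands as a limit on the size of the point. It does not remove the point, because the plan gives no ground for assuming the SD is negligible: sessions run in class across several schools, and the intervention is adapted to developmental level.

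**Conclusion.** The point holds as a recommendation that should be adopted. It does not show that the planned analysis is invalid.

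The firmest part is precision: against a change-based ANOVA, baseline adjustment lowers the true standard error by about 6% to 16% for correlations of 0.75 to 0.4, with data already being collected. Omitting classroom and sex matters little by itself for the change contrast, at about 1% to 3%, if the arm effect is constant across classes.

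The error-rate part is conditional. With a between-class SD of 0.2 to 0.3 and 40 classes of 22, pupil-level type I error is about 7% to 11% for arm-by-age. For the main effect it is about 7% to 10%, and only if inference extends to other classes. At SD 0.1 or less the inflation is not material. Class numbers, class sizes, ICCs, correlations and effect variation are all assumptions, because the documents give none.

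**What to change.** In section IV, name one multilevel model as the main analysis for each outcome:

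- Follow-up scores regressed on arm, wave, arm-by-wave, baseline score and sex, with classroom as a random intercept or fixed stratum and allowance for the correlation of a pupil's repeated scores.
- For arm-by-age in Aim 3, add a random arm slope by classroom, or regress class-specific arm differences on class age.
- For the main effect, report the random-slope model as a sensitivity analysis. Putting the slope on the age test alone would leave the same issue open for the main effect.
- Keep mixed ANOVA for description only.
- State in section III whether gender blocking was done within each classroom, so that the model can match the strata actually used.

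The cost is SAP wording and a little more analysis work. Multilevel software is already listed, and baseline scores, sex and classroom should be available for every randomised pupil. The one statistical price is a slightly wider interval for arm-by-age if effects do vary between classes, which is the honest width in that case.

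### Does assignment in class by researchers, with research assistants running the sessions, contradict the double-blind claim and leave allocation unprotected?

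*Combined protocol and SAP*

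**What the plan says.** Under III. Methods, Study design and participants, the combined protocol and SAP states: "We will conduct a double-blind randomized controlled trial (RCT) with two parallel groups". The planned size is about 900. On the unit of allocation it says: "Group assignation will be done at the individual level within each classroom". The ratio is 1:1, blocked by gender, and then: "They were assigned to their allocated group in class by the researchers".

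Under Procedure: "Both interventions and assessment measures will be administered by research assistants during normal class time and last around 50 minutes". Under Measures, on the main outcomes: "Depressive symptoms and aggressive behavior will be assessed by means of self-reports".

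The document does not name the blinded parties. It does not say who generates or holds the sequence, what the block size is, how the next assignment is hidden, or whether staff who deliver or assess know the arm.

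**The concern.** A double-blind trial normally keeps both the participant and at least one group of staff unaware of the arm. Here the only staff actions described are assigning pupils and running sessions, which are the steps at which the arm is most easily seen. The two writing tasks also differ in content: one is a narrative about people's capacity to change, the other a letter about the brain and a new school building. Anyone who reads over a pupil's shoulder could tell them apart.

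If staff could see or choose the assignment, two things would be at risk. Randomisation would no longer guarantee comparable groups, because a pupil judged likely to benefit could be given the active task. Staff could also encourage one arm more than the other during the writing exercise. The protocol's introduction describes average effects of universal depression prevention as small, so even a modest distortion could matter. A double-blind label would then claim more than the trial delivered.

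**Working it through.** **Step 1: set the statements side by side.**

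| Point | What the document gives | What it leaves open |
|---|---|---|
| Blinding | Declared double-blind | Which parties |
| Allocation | Individual, within classroom, 1:1, blocked by gender | Sequence generation, custodian, block size |
| Handing out | By the researchers, in class | Whether they could see or alter the assignment |
| Delivery and assessment | By research assistants | Whether they are the same people at both, whether they are the researchers who assign, whether they know the arm |
| Outcomes | Pupil self-report; hormones assayed by a laboratory | Nothing relevant here |

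No cell in the middle column contradicts another. Pupils are assigned to a group already described as allocated, which is how one would describe giving out coded or sealed materials, or starting a computer task with hidden assignment. It would also describe an open list. The text does not settle which.

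**Step 2: trace the routes by which staff knowledge could bias the comparison.**

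- *Selective enrolment.* Consent and the first survey come a week before the intervention (Procedure). This limits the route, although the date of randomisation is not given.
- *Outcome rating.* Staff do not rate depression or aggression. Measures are anonymous (Procedure), and the matching code is said to be known only to the pupil (Ethical considerations). Nothing suggests that staff at the six-month or one-year wave could tell a pupil's arm.
- *Facilitator quality.* Allocation is within the classroom. If both arms sit in one room, they share the same staff, so a better or worse facilitator affects both arms alike. Only different handling of individual pupils remains.
- *Different handling in the session.* Both tasks have the same three parts, and the control was built to mirror the active one (Preventive Intervention). No coaching role is described.
- *Steering who gets which task.* This depends wholly on concealment, on which the document is silent.

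**Step 3: the size.** The document has no sample-size calculation to reproduce. Its only input is n = 900. Assume two-sided alpha of 5%, power of 80%, equal arms, no dropout, no clustering and no baseline adjustment. The smallest detectable standardised difference on a single follow-up score is then

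(1.960 + 0.842) × √(4/900) = 2.802 × 0.0667 = 0.187 SD.

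Assume further a staff-induced difference of 0.05 to 0.10 SD:

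- 0.05 / 0.187 = 0.27
- 0.10 / 0.187 = 0.54

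The arithmetic is correct, but the numerator has no source in the document. The ratio compares an assumed bias with a detectable difference. It does not estimate what share of any observed effect would be bias.

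**The case for a change.** The strongest reply is that participant blinding has visible support (unobtrusive presentation and a matched control) while the second blind has none. The data system also describes no allocation log. Completed tasks are matched to questionnaires through data the pupils supply, so a pupil handed the wrong task would be recorded by what was received, and nothing in the plan would reveal the switch. Concealed allocation therefore matters more here than in a trial with named records, and describing it would take a sentence or two.

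Most of this stands as a description of what is unwritten. A reader cannot verify the second blind from the text, and the trial report should say who was blinded, how the sequence was made and hidden, and what delivery staff could see. It does not establish that allocation was open or that staff knew the arm.

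A remedy of numbered sealed booklets has its own difficulty. The document does not say the tasks are on paper, and it describes the earlier US single-session version as computer-delivered. The allocation sentences are in the past tense, so the step may already have been taken. Prescribing packs might only restate what was done, or might not fit the medium used.

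**Conclusion.** The concern does not hold as a defect in the design. The double-blind label and the described procedure sit uneasily together, but the conclusion that staff were unblinded and allocation unprotected is drawn from silence. A team that follows the plan as written, with individual randomisation, double-blinding and parallel tasks, would have to conceal the assignment to do so, and would get a sound comparison. What is missing is reporting detail, and it belongs in the account of how the trial was run.

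No size can be attached to the bias. The 27% to 54% range rests on an assumed 0.05 to 0.10 SD effect and should carry no weight.

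This conclusion assumes that the team carried out the double-blind design it declares. If the trial's records showed that staff chose or could foresee assignments, the judgement would change, but nothing in the document says they did.
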